9.6 DEMOGRAPHIC AND BASELINE CHARACTERISTICS

Demographic and baseline characteristics will be presented descriptively.

9.7 SUBGROUP ANALYSES

The study will encourage participant enrollment to be inclusive of all populations as defined by demographic factors such as race, ethnicity, gender identity, age, and by the presence of certain clinical characteristics such as multiple comorbidities. Subgroup analyses will be accounted for by including potential subgroups as covariates in Model 3 (see Section 9.1 Primary Endpoint). [REDACTED]

9.8 HANDLING OF MISSING VALUES

According to the schedule of events, patients are expected to attend visits at baseline, Week 4, and Week 8. No explicit imputation will be performed; the MMRM model described above will be run on the ITT population, which implicitly imputes missing data under a missing at random (MAR) assumption.

To examine the impact of intermediate missing values and missing values after early withdrawal from the study, sensitivity analyses including multiple imputations will be performed. Missing safety data will not be imputed.

9.9 INTERIM ANALYSIS

After 50% of the planned participants have completed the study (been evaluated after 8 weeks on treatment) an interim analysis will be conducted on blinded data by an independent statistician to verify that the effect size estimates used to plan the study sample remain reasonable and, if needed, calculate a new required sample given the updated effect size estimates. Specifically, the clinically important difference (CID) analyses (described in section 7.2 of the SAP) will be performed on the interim HAM-D6 data to determine whether clinician judgments of category differences in the HAM-D6 in the context of use of PPD (Δ) are consistent with a priori expectations of a 3-point CID for MDD. Additionally, the SD of the difference between baseline and Week 8 will be calculated to determine whether it is in line with expectations for detecting a 3-point (or Δ) difference between arms with $\alpha = .05$, two-tailed and $1-\beta = .80$, i.e., $n / \text{arm} \geq 2^*(z_{\alpha/2} + z_{1-\beta})^2 * \text{SD} / \Delta = 2^*2.8^2 * \text{SD} / \Delta = 15.68 * \text{SD} / \Delta$.

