I agree to conduct this study according to this protocol and to comply with its requirements, participant to ethical and safety considerations and guidelines, and to conduct the study in accordance with the Declaration of Helsinki, International Council for Harmonisation guidelines on Good Clinical Practice, and applicable regional regulatory requirements.

I agree to comply with the procedures described for data recording and reporting and to permit monitoring and auditing by Woebot Health and inspection by the appropriate regulatory authorities.

I agree to make my participants' study records available to Woebot Health personnel, their representatives, and relevant regulatory authorities in order to verify data that I have entered the case report forms. I will retain the study-related essential documents until Woebot Health indicates that they are no longer needed. I am aware of my responsibilities as an investigator as provided by Woebot Health.

I understand that Woebot Health may decide to suspend or prematurely terminate the study at any time for whatever reason; such a decision will be communicated to me in writing. Conversely, should I decide to withdraw from execution of the study, I will communicate my intention immediately in writing to Woebot Health.

Investigator Name (Print)	Title
Institution:	
Signature:	Date

PROTOCOL SYNOPSIS

Sponsor Name: Woebot Health

Protocol Number: WB001-001

Protocol Number: WB001-001

Full Title: A Multicenter, Randomized, Double-Blind, Controlled Study Evaluating the Efficacy and Safety of a Digital Therapeutic WB001 as an Adjunct to Treatment as Usual Among Women with Mild to Moderate Postpartum Depression

Abbreviated Title: [Study Evaluating the Efficacy and Safety of WB001 as an Adjunct to TAU in Postpartum Depression]

Sponsor: Woebot Health

Coordinating Investigator: [TBA]

Study Type: Interventional

Planned Number of Subjects: 210, with interim analysis for sample size re-estimation

Study Sites: Up to 25 study centers within the U.S.

Primary Objectives: The purpose of the study is to determine whether, for women diagnosed with PPD, WB001 with adjunctive Treatment as Usual (TAU; WB001+TAU) can reduce symptoms of depression compared to an educational control with adjunctive TAU (Ed Control “ED001” +TAU), at the end of treatment (EOT; 8 weeks) as measured by the HAM-D6.

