- Must have current mild-moderate depression as measured by the HAM-D6 score > 7 and < 13 (i.e., between 8-12, inclusive) at screening (Bech et al., 2007; Pridmore et al., 2020)
- Participant must confirm having a form of TAU, defined as clinician supervised outpatient care management and includes follow-up visits, medication, psychotherapy, or some combination thereof
- As part of TAU during the study, any confirmed concomitant medications and/or psychotherapy are permissible and must be regularly scheduled or stable (dose and frequency) for over 4 weeks prior to baseline (BL) visit

Key Exclusion Criteria:

- Gestation less than 28 weeks
- HAM-D6 score ≤ 7 or ≥ 13 (severe depression) at Screening
- Currently pregnant or plans to become pregnant within the next 8 weeks
- History of drug and/or alcohol use disorder within the past 12 months measured by the SCID-5-CT (Williams JB, 2015)
- Lifetime history of suicide attempt or ideation with a plan and intent to harm oneself during the current episode of PPD
- Current or lifetime psychosis, including history of post- and peri-partum psychosis as measured by the SCID-5-CT (Williams JB, 2015)
- Current or lifetime history of schizophrenia, schizoaffective disorder, bipolar disorder, and/or homicidal or infanticidal ideation as measured by the SCID-5-CT (Williams JB, 2015)
- History of antidepressant treatment with ketamine/esketamine, electroconvulsive therapy, vagal nerve stimulation, or a deep brain stimulation device
- Fetal demise within the past 18 months
- Previous Woebot use

Study Conditions: 1:1 randomization to either [WB001+TAU] or [ED001+TAU]

Control Device: The educational control application is an educational app named ED001.

Sponsor Name: Woebot Health

Protocol Number: WB001-001

Treatment as Usual (TAU): Participants will receive TAU, which is clinician supervised outpatient care including follow-up visit(s), psychotropic medication, psychotherapy, or some combination thereof.

Primary Endpoint: Difference in HAM-D6 scores between groups at EOT, controlling for baseline (BL) and other covariates

Secondary Endpoints:

1. Difference between arms in the following assessments at EOT, controlling for BL and other covariates:

- Edinburgh Postnatal Depression Scale (EPDS)
- Maternal-Infant Bonding Scale (MIBS)
- Patient Health Questionnaire-9 (PHQ-9)
- Generalized Anxiety Disorder-7 (GAD-7)

2. Difference in HAM-D6 scores within arms between BL and EOT

Exploratory Endpoints:

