8. STATISTICAL ANALYSIS

8.1 GENERAL METHODOLOGY

Analyses will be performed using SAS® (SAS Institute, Cary, NC, US) and R (R Core Team (2021). R Foundation for Statistical Computing, Vienna, Austria. <https://www.R-project.org/>). Each analysis will be conducted by a blinded statistician, and the statisticians will not confer until QC. The DSMB statistician will be unblinded and generate the randomization schedule. The interim re-estimation of sample size will be conducted by blinded pair programming, as with the main analysis. All personnel involved with the analysis of the study will remain blinded until database lock and identification of protocol deviations, unless otherwise mentioned in the protocol (e.g., DSMB statistician performing randomization and analysis requested by DSMB members).

The statistical analysis plan (SAP) will be approved prior to the interim analysis performed by the blinded independent statistician, and otherwise prior to any lock of the study database and unblinding of the study data. The SAP will provide a detailed description of the statistical methods and expand on the details provided in the protocol.

All data will be presented by treatment group. Descriptive statistics (number of observations, mean, standard deviation [SD], median, interquartile range [q25 and q75], and range [minimum and maximum]) will be provided for continuous variables, and counts and percentages will be presented for categorical variables.

Baseline is defined as the last non-missing measurement before or on the date of first use of the investigational device.

Sponsor Name: Woebot Health

Protocol Number: WB001-001

All statistical tests will be 2-sided and performed at the 0.05 level of significance unless stated otherwise. Descriptive analyses and p-values will be presented for exploratory endpoints.

Checks of assumptions (e.g., normality) underlying statistical procedures will be performed and appropriate corrective procedures will be applied (e.g., transformation or nonparametric tests) prior to statistical testing.

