8.3 SAMPLE SIZE DETERMINATION

The concept of a minimally important difference (MID) for depression rating scales are not yet widely established. However, both researchers and a growing number of clinicians who are using measurement-based care employ standardized symptom rating scales to determine whether treatments for depression and other conditions are working effectively (Rush et al., 2021). The degree of symptom improvement that is meaningful

Sponsor Name: Woebot Health

Protocol Number: WB001-001

to patients remains unclear. However, a recent analysis based on Brexanolone, an FDA-approved PPD-specific treatment based on HAM-D, provided the first estimates of PPD-specific MID and meaningful change threshold (MCTs) for the HAM-D in this clinically important outcome. It concluded that a 2–3 point change in the HAM-D6 is clinically meaningful and a 4–7 point change is clinically substantial (Rush et al., 2021). A second analysis based on two randomized controlled trials in 482 adult patients with MDD suggested a 2-point difference on the HAM-D6 will allow detection of a change in depression category as mild and moderate and defined as a scores of 8–9 and 10–12, respectively (Ruhe et al., 2005). Thus, as an adjunct to TAU, a 3-point change was identified as an a priori clinically meaningful difference for WB001 to demonstrate a reduction of depression for mild and moderate PPD (for additional justification for use of the HAM-D6 as the primary endpoint see Section 9.1 Primary Endpoint).

[REDACTED]

Simulations using this RCT study data were conducted to determine the power of various sample sizes to detect a 3-point difference in HAM-D6 score between the treatment and control groups at Week 8, controlling for relevant baseline factors and considering potential for additional variability within the study.

[REDACTED]

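### The interim sample-size rule in section 9.9 does not protect its stated 80% power for 3 points: the ratio SD/Δ is not squared, and an interim Δ may replace 3 with no visible floor on N

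*Combined protocol and SAP*

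**What the plan says.** The synopsis plans "210, with interim analysis for sample size re-estimation", allocated 1:1. Section 8.3 sets the target: "a 3-point change was identified as an a priori clinically meaningful difference for WB001". It says of the basis for N: "Simulations using this RCT study data were conducted to determine the power of various sample sizes to detect a 3-point difference in HAM-D6 score". The text around that sentence is redacted, so the planning SD, power and dropout rate cannot be seen.

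Section 9.9 places the interim after 50% of planned participants have been evaluated at 8 weeks, on blinded data. It does two things.

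- It runs a clinically important difference (CID) analysis on the interim HAM-D6 data, to see whether clinicians' category judgments in PPD give a Δ that is "consistent with a priori expectations of a 3-point CID for MDD".
- It calculates the SD of the baseline to Week 8 difference "to determine whether it is in line with expectations for detecting a 3-point (or" Δ) difference, at two-sided 0.05 and 80% power. The printed requirement is n per arm ≥ 2·(sum of the two z values)²·SD/Δ = 15.68·SD/Δ.

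The section then provides for the sponsor to "calculate a new required sample given the updated effect size estimates" if needed. The visible text does not say when Δ replaces 3, whether N may fall, or whether n counts enrolled or evaluable participants.

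**The concern.** A re-estimation rule should preserve the power the trial claims for the difference it has chosen. Two features of section 9.9 work against that.

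First, the two-sample formula for means needs the square of SD/Δ. Without it, n is too small whenever SD exceeds Δ, even if Δ stays at 3.

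Second, the 3 points are described as fixed in advance, yet the sizing step accepts a Δ estimated from the trial's own data. If that estimate is above 3 and N is reduced, the trial may end up underpowered for the difference that section 8.3 calls meaningful. At stake is whether 80% power for 3 points remains a property of the design after the interim.

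**Working it through.** **Inputs from the protocol.** N = 210, so 105 per arm (synopsis). Two-sided α = 0.05 (8.1 and 9.9). Power 0.80 (9.9). Target 3 points (8.3). Interim at 50%, so 105 evaluated, about 52.5 per arm (9.9). HAM-D6 range 0 to 22 (5.2). Entry score 8 to 12 (4.1).

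**Assumed.** The change-score SD is not visible, so a range of 4 to 8 is shown.

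**The plan's own figures.** The constant reproduces: 2 × 2.8² = 15.68 (15.70 with exact z values). The 210 cannot be reproduced, because it rests on simulations whose inputs are redacted.

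**Step 1: printed against standard formula, Δ = 3.** Power = Φ(3 / (SD·√(2/n)) − 1.96).

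| SD | Printed 15.68·SD/3 | Power at that n | Squared 15.68·(SD/3)² | Power at 52.5 per arm | Power at 105 per arm |
|---|---|---|---|---|---|
| 4 | 21 | 68.1% | 28 | 97.0% | over 99.9% |
| 5 | 27 | 59.7% | 44 | 86.7% | 99.2% |
| 6 | 32 | 51.6% | 63 | 72.6% | 95.2% |
| 7 | 37 | 45.4% | 86 | 59.3% | 87.4% |
| 8 | 42 | 40.5% | 112 | 48.5% | 77.6% |

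Example at SD 7: 15.68 × 7/3 = 36.6, so 37; 15.68 × (7/3)² = 85.4, or 85.5 with exact z values, so 86.

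**Step 2: can the printed rule ask for an increase?** To require 105 per arm at Δ = 3 it needs SD = 105 × 3/15.68 = 20.1. With entry scores of 8 to 12 and Week 8 scores of 0 to 22, change lies between −12 and +14. That range of 26 caps the SD at 13, where the printed rule gives 15.68 × 13/3 = 68 per arm. So it can never call for more than 105 per arm at Δ = 3, although at SD 8 the correct figure is 112. It reaches the 52.5 per arm already evaluated only at SD = 52.5 × 3/15.68 = 10.0. Below that it reports that the participants already evaluated are enough.

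**Step 3: replacing 3 by Δ, with the squared formula.** n changes by (3/Δ)²: 9/16 = 56% at Δ = 4, and 9/4 = 2.25 times at Δ = 2. The final N cannot fall below the 105 already evaluated. They give 80% power for 3 points when SD = 3·√(52.5/15.70) = 5.49. So a shortfall by this route needs Δ above 3, a cut in N, and SD above about 5.5.

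Example at SD 7, Δ = 4: 15.70 × (7/4)² = 48.1, so 49 per arm. This is below 52.5, so the 105 already evaluated set the size: power for 3 points is 59.3%, against 87.4% at 210. Participants still in follow-up at the interim would raise the 59.3% somewhat.

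If Δ = 2, n at SD 6 becomes 142 per arm and power for 3 points is 98.8%. Power is not harmed.

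**The case against.** **In favour of the plan.** Δ is a clinician-anchored CID on blinded data, not the observed treatment effect, so this is not unblinded effect-size re-estimation and no type I error problem follows from it. Section 8.3 says meaningful differences for depression scales are not yet widely established, and 9.9 describes the 3 points as a value for MDD. Checking it in PPD is a reasonable aim. The rule is written as a minimum, applies only if needed, and nowhere says enrolment will be cut. The missing square may be a typing slip or an extraction loss. All this stands as far as it goes. But the squares on the z sum and on 2.8 survive in the same line while SD/Δ appears three times without one, so lost formatting is unlikely; the PDF should be checked. A legitimate CID analysis need not feed the sample size.

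**Stronger readings that the documents do not support.**

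- A reader might infer that resetting Δ to 4 or 5 drops power for 3 points to about 56% or 39%. Those are formula-only values. Because 105 participants are already evaluated, they need SD of at least about 7.3 and 9.1 respectively.
- A reader might infer from N = 210 that the planning SD was above 5.5. Solving back, 80% power gives SD 7.76 with no dropout and 6.94 with 20%. But N came from simulations that controlled for baseline factors and allowed for added variability, at a power that is not visible, so this indicates little.
- A reader might infer that n is the enrolled number, so that 10%, 20% or 30% missing Week 8 data takes power to about 76%, 71% or 65%. Section 9.9 does not say enrolled, section 4.6 allows withdrawals to be replaced, and the redacted part of 8.3 may hold an allowance. A pooled blinded SD also gives some slack: a true 3-point effect adds 3²/4 = 2.25 to the variance, which is 6% more n at SD 6 (2.25/36). Replacement is still not a full answer. Under 3.4 and 4.7 a participant with Week 4 but no Week 8 data can count as a completer rather than a withdrawal, and the note to Table 4 removes some participants from the primary analysis.

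**Conclusion.** The point holds in two parts of different strength.

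The formula is wrong as printed. At SD above 3 it undersizes even with Δ held at 3, and within the possible range of scores it cannot detect that 105 per arm is too few. This depends on no planning value, only on the print being faithful to the PDF.

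The replacement of 3 by an interim Δ is a gap in the rule with conditional harm. It costs power for 3 points only if Δ exceeds 3, N is then reduced, and SD exceeds about 5.5. Since no SD is visible, neither the likelihood nor the size of a shortfall can be established. The absence of a floor and of an attrition term can be asserted only of the visible text, because 8.3 is partly redacted and SAP section 7.2, which 9.9 cites, was not available.

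The power figures use a normal approximation, equal arms and an unadjusted change score. Baseline adjustment in the planned repeated-measures model could improve them.

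**What to change.** In section 9.9, and in the SAP to match:

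- Print n per arm ≥ 15.68·(SD/Δ)².
- Keep Δ = 3 for sizing and update only the blinded SD.
- State that N may stay at or rise above 210 but not fall.
- Report the CID analysis for interpretation only.
- Define n as the number evaluable at Week 8, and divide by (1 − observed proportion missing at Week 8), unless redacted or unsupplied text already does this.

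With 210 evaluable as the minimum, power for 3 points is 95.2% at SD 6 and 87.4% at SD 7; at SD 8 the corrected rule would ask for 112 per arm. The change is to wording only. The sponsor gives up the option of reducing N at the interim.

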3. STUDY DESIGN

3.1 OVERALL STUDY DESIGN

This is a multicenter, double-blind, randomized, controlled trial to evaluate the efficacy and safety of WB001 in adult women with mild to moderate PPD. Eligible participants must have diagnosis of mild to moderate PPD and experience at least mild to moderate symptom severity as evidenced by a score of > 7 and < 13 (i.e., between 8-12, inclusive) on the HAM-D6.

The study will utilize referrals by an obstetrician, pediatrician, or other healthcare professional, or by other digital and site based recruitment methods and direct participants to the closest study site, across up to 25 study centers in the U.S., to schedule and complete a pre-screening/screening appointment. From there, the site staff will schedule their first office visit, during which the site staff with oversight by the investigator, will obtain informed consent and complete the screening and BL assessments. The CIR will be responsible for administration of the HAM-D for the primary endpoint as outlined in [Appendix 3: Schedule of Events](#). To standardize and facilitate administration of the primary endpoint, the Structured Interview Guide for the Hamilton Depression Rating Scale (SIGH-D) will be used (Williams, J.B. 2015).

Participants will then be randomized in a 1:1 manner to either [WB001+TAU] or [ED001+TAU] and will be prompted to install the app on their smartphone. Study site personnel will help the participants with the app installation to streamline enrollment. Participants in both groups will participate in a form of TAU, which is clinician supervised outpatient care including, follow-up visit(s), psychotropic medication, psychotherapy, or some combination thereof. [REDACTED]

[REDACTED] Both treatment arms will be presented as possibly helping to improve PPD and both will be described as the study app so that there is no distinction made to the participants about WB001 or the digital educational control app. Post-randomization, the 8-week treatment period begins when the participant successfully downloads the study app and completes the integrated onboarding process.

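### The interim re-estimation formula in section 9.9 omits the square on SD/Δ, so at a difference of 3 or 2 points it can never ask for more than the planned 105 per arm

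*Combined protocol and SAP*

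**What the plan says.** The synopsis gives the planned number of subjects as "210, with interim analysis for sample size re-estimation", randomized 1:1, so 105 per arm. Section 8.3 bases that number on simulations run to "determine the power of various sample sizes to detect a 3-point difference in HAM-D6 score"; the inputs and results are redacted.

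Section 9.9 sets the timing of the interim: "After 50% of the planned participants have completed the study (been evaluated after 8 weeks on treatment". A blinded independent statistician is to check the planning estimates and, "if needed, calculate a new required sample given the updated effect size estimates". Two quantities are examined: the clinically important difference on the HAM-D6, and the SD of the change from baseline to Week 8. The SD is judged against what is needed for "detecting a 3-point (or Δ) difference between arms" at two-sided α = 0.05 and power 0.80. The per-arm requirement is written as a chain of three expressions that ends in "2^*2.8^2 * \text{SD} / \Delta = 15.68 * \text{SD} / \Delta". No other re-estimation formula is readable in the documents.

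**The concern.** The number per arm needed to compare two means grows with the square of SD/Δ. In section 9.9 that ratio appears to the first power in all three expressions, while the squares on the z-sum and on 2.8 are printed. Reading SD as a variance does not repair it, because Δ would still have to be squared.

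The formula decides whether the trial is enlarged. If it understates the requirement whenever SD exceeds Δ, statisticians who follow the plan exactly would report that 105 per arm is enough when it is not. The trial would then continue with less than 80% power for its primary endpoint.

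**Working it through.** **Inputs from the documents.** Two-sided α = 0.05 and power 0.80 (section 9.9). Δ = 3 (sections 8.3 and 9.9). Planned N = 210 at 1:1, so 105 per arm (synopsis). HAM-D6 range 0 to 22 (section 5.2). Entry requires "a score of > 7 and < 13 (i.e., between 8-12, inclusive) on the HAM-D6" (section 3.1), and screening and baseline assessments fall on the same day (Appendix 3).

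**Assumed.** No planning SD is readable, so a range of SDs is shown. Δ = 2 is also shown, because section 9.9 lets the interim estimate replace 3, and section 8.3 takes 2 as the lower end of the range for which a "point change in the HAM-D6 is clinically meaningful".

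**The plan's own figure.** 2 × 2.8² = 15.68. With unrounded z values, 2 × (1.960 + 0.842)² = 15.70. The multiplier is reproduced.

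**The two forms.** Printed: n per arm = 15.68 × SD/Δ. Correct: n per arm = 15.68 × (SD/Δ)². They agree at SD = Δ. Above that the printed form is too small by the factor SD/Δ; below it, too large. Results are rounded up; power is from the noncentral t distribution, two-sided 0.05.

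| Δ | Assumed SD | Printed n/arm | Correct n/arm | Power at 105/arm |
|---|---|---|---|---|
| 3 | 2 | 11 | 7 | >99% |
| 3 | 4 | 21 | 28 | >99% |
| 3 | 5 | 27 | 44 | 99% |
| 3 | 6 | 32 | 63 | 95% |
| 3 | 8 | 42 | 112 | 77% |
| 3 | 10 | 53 | 175 | 58% |
| 2 | 5 | 40 | 98 | 82% |
| 2 | 6 | 48 | 142 | 67% |
| 2 | 8 | 63 | 251 | 44% |

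As an example, SD 6 and Δ = 2 give 15.68 × 6/2 = 47.04 as printed and 15.68 × (6/2)² = 141.12 when squared.

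**Largest n the printed form can return.**
- With baseline between 8 and 12 and Week 8 between 0 and 22, change lies between 0 − 12 = −12 and 22 − 8 = +14.
- An SD cannot exceed half the range, here (14 + 12)/2 = 13.
- At that limit the printed form gives 15.68 × 13/3 = 67.9, so 68 per arm, and 15.68 × 13/2 = 101.9, so 102 per arm. Using an n − 1 divisor for the SD adds at most one per arm.
- To reach 105 it would need SD = 3 × 105/15.68 = 20.1 at Δ = 3, or 2 × 105/15.68 = 13.4 at Δ = 2. Neither is attainable.
- It can pass 105 only if Δ is revised below 15.68 × 13/105 = 1.94.

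**When an increase is really needed.** The correct form reaches 105 per arm at SD = 3 × √(105/15.68) = 7.76 for Δ = 3, and at SD = 2 × √(105/15.68) = 5.18 for Δ = 2.

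**The case against.** The strongest reply is that little would change at Δ = 3. An increase is needed there only above an SD of 7.76, which is large for this population. If Week 8 scores were spread evenly over all of 0 to 22, independently of baselines spread evenly over 8 to 12, the SD of change would be √((23² − 1)/12 + (5² − 1)/12) = 6.8, and the correct form would ask for 81 per arm. Up to about SD 7.7 both forms therefore lead to the same decision to keep 105. Nothing in the text allows N to be reduced, so a printed answer well below 105 does no harm by itself. This stands, and it limits the consequence at Δ = 3. With an assumed 20% dropout, 84 per arm remain and the threshold falls to 6.9.

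It does not carry over to Δ = 2. There the threshold is 5.18, close to the SD of 5.1 given by Week 8 scores spread evenly over only 0 to 16. The even spread over the full scale would need 181 per arm. Whether the interim would move Δ to 2 is unknown.

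Two further points concern what cannot be seen. The SAP may state the formula correctly, and section 8.1 has the re-estimation programmed independently in duplicate. But no SAP text is readable, and two programmers who code the same printed line will agree on the same wrong answer. The equation was also machine-read, and the stray superscript after the leading 2 shows some misreading. Losing the same exponent three times while keeping two others is unlikely, but the source PDF should be checked.

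**Conclusion.** The formula is wrong as printed. At Δ = 3 it understates the requirement once SD exceeds 3, and at Δ = 3 or Δ = 2 no SD that eligible participants can produce would make it ask for more than 105 per arm. As a safeguard against an underestimated SD it cannot work.

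The decision itself goes wrong when the SD of change exceeds 7.8 at Δ = 3, which would be unusual, or 5.2 at Δ = 2, which is less so. In the assumed cases power at 105 per arm would be 77% (Δ = 3, SD 8) or 67% (Δ = 2, SD 6), before dropout.

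The finding rests on the equation having been read correctly and, for the upper limit, on the entry range of 8 to 12. It does not depend on the redacted planning SD and does not show that 210 is too small, since that number came from simulations. It should be corrected before the interim, because it is a prespecified rule for a sample-size decision.

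**What to change.** First confirm the equation against the source PDF. Then replace the line in section 9.9 with n per arm ≥ 2(z_α/2 + z_1−β)² × (SD/Δ)² = 15.68 × (SD/Δ)², and make the same change wherever the SAP repeats it. Stating the SD expected at planning next to the formula would give the interim value something to be compared with.

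The cost is one corrected line, plus the matching SAP text. It adds no patients unless the interim SD and Δ put the correct requirement above 105 per arm.
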